Title: Utility of Restrata With Split Thickness Skin Graft to Reconstruct the Forearm Donor Site

NCT Number: NCT04829331

ID: 21-RES-003

Document Date: 22 APRIL 2021

Title:

Utility of Restra (Acera Surgical Inc., St. Louis, MO) in forearm flap reconstruction with donor site healing and function.

Objective:

Understand association between use of Restra (Acera Surgical Inc., St. Louis, MO) in forearm flap reconstruction with donor site healing and function.

Hypothesis:

Use of Restra in combination with split-thickness skin graft for reconstruction of forearm flap reconstruction donor site will be associated with decreased occurrence of tendon exposure at four weeks post-operatively when compared to split-thickness skin graft alone.

Design:

Randomized controlled trial.

Setting:

Single institution, Nebraska Methodist Medical Center

Population:

Adult patients undergoing radial forearm free flap or ulnar forearm free flap at a single institution.

Intervention:

Reconstruction of forearm harvest site using Restra with a split-thickness skin graft.

Control:

Reconstruction of forearm harvest site using split-thickness skin graft alone.

Inclusion Criteria:

1. All patients age 19 or greater that will undergo radial forearm free flap or ulnar free flap.
2. Photo documentation of wound bed at two weeks and four weeks must be obtainable either by physician or patient.

Exclusion Criteria:

1. Active systemic immunosuppression (active use of high-dose steroids ($\geq 40\text{mg}$ prednisone daily or equivalent) or other immunosuppressive medications OR medical conditions causing immunosuppression, i.e. human immunodeficiency virus etc).
2. Diabetes mellitus with most recent Hemoglobin A1c ≥ 10.0 within 30 days prior to surgery.
3. Morbid obesity (BMI >40).
4. Inability to maintain wrist immobilization for full planned period.
5. Severe malnutrition (prealbumin levels <10 mg per dL within 30 days prior to surgery OR BMI <15 (very severely underweight)).
6. Other conditions felt to significantly impair wound healing per surgeon discretion.

Primary Outcomes:

1. Tendon exposure at four weeks post-operatively (Yes/No).

2. Percentage of surface area of split-thickness skin graft incorporation at four weeks post-operatively.

Secondary Outcomes:

1. Tendon exposure at two weeks post-operatively (Yes/No).
2. Percentage of surface area of split-thickness skin graft incorporation at two weeks post-operatively.
3. Aesthetic appearance of donor site per surgeon rating (graded 1-10).
4. In patients with tendon exposure, time to complete wound epithelialization (measured as time from surgery to first documentation of complete epithelialization in days).
5. Need for re-operation on forearm or secondary wound care strategy after tendon exposure.
6. Forearm infection requiring surgical drainage and/or antibiotics.

Goal Enrollment:

40 total patients with 1:1 group enrollment. Power analysis was performed to identify necessary sample size to detect an absolute reduction of tendon exposure at four weeks of 15% (25% baseline, 10% expected rate with intervention with power of 80% and alpha 0.05). Under these assumptions, 100 patients would need to be recruited into each arm. Recent historical review of institutional volume demonstrates a rate of approximately 35 forearm flaps annually (2019-2020 data). Assuming a 70% study enrollment rate, we would meet enrollment goals in approximately eight years. This time commitment is felt by the study authors to exceed what is reasonable without first generating preliminary data. The proposed sample size is therefore practically derived based annual surgical volume at this institution and available resources from our industry partner. We recognize the limitations in this study, therefore, and that this design is not truly hypothesis testing. Using the above assumptions, we expect goal enrollment to be met within approximately 18 months.

Covariates Recorded:

1. Demographic data - Age, sex, race, ethnicity, BMI.
3. Medical history - Modified frailty index - 5, diabetes mellitus, coronary artery disease, peripheral artery disease, immunosuppression.
4. Social history - Smoking status (current/former/never, total py), alcohol use pattern
5. Wound surface area in square cm.

Randomization:

Occurs when the patient is scheduled for surgery. A simple randomization strategy will be utilized by creating a randomization list using <https://www.graphpad.com/quickcalcs/randomize1/>, which will ensure equal group distribution. The surgery scheduler will assign patients to their category based on this pre-determined list in consecutive order based on date of surgery scheduling request rather than surgical date to minimize risk of bias.

Consent:

Written informed consent will be obtained at the time of study enrollment and will be stored securely by the Methodist research office. This form is separately attached.

Protocol:

1. All forearm and ulnar flaps will be harvested using a suprafascial harvest technique.
6. Surgical technique for application of Restrata with split-thickness skin graft.
 1. Restrata will be meshed in a 1:2 fashion to allow for egress of serous fluid and minimize risk of fluid collection.
 2. Restrata will be applied to the entire wound bed not amenable to primary closure and will be underlaid beneath the surrounding skin edges.
 3. A split-thickness skin graft is harvested from patient's thigh at 15:1000 inches and placed on top of the Restrata to cover the entire wound bed. The graft is sutured in place using suture choice of surgeon's preference.
 4. Ultrasound gel is applied to the graft and matrix.
 5. Xeroform gauze bolster is placed over the wound and secured using suture choice of surgeon's preference.
 6. The wrist is wrapped with kerlix gauze and the wrist is immobilized
7. Bolsters are removed at five days, the wound is inspected, and high-definition digital photographs are obtained.
8. The arm remains immobilized for two weeks, and daily xeroform dressing changes are performed by patients, family, or home health per treatment team discretion.
9. Immobilizers are removed at initial follow-up visit at two weeks and high-definition digital photographs are obtained. (Any visit between 12 and 16 days will be considered acceptable as two-week follow-up).
10. If graft incorporation is adequate at two-week follow-up per treating physician discretion, Vaseline® or alternative non-antibiotic ointment will be applied to the graft edges between two and four-week follow-up visits by patients, family, or home health per treatment team discretion. If graft failure occurs by two-week follow-up, Aquacel Ag (ConvaTec Medical Group. Deeside, UK) will be applied to the areas of graft failure as the primary treatment strategy with daily dressing changes.
11. High-definition digital photographs are obtained at four-week follow-up.
12. If graft incorporation is adequate at four-week follow-up per treating physician discretion, no additional wound care will be performed. If graft failure occurs by four-week follow-up, Aquacel Ag will be applied to the areas of graft failure as the primary treatment strategy with daily dressing changes.
13. If at any point the treating physician feels that the primary treatment strategy is inadequate or inappropriate, a secondary wound care strategy (alternative treatment, negative pressure therapy, surgical debridement, repeat grafting, etc) may be pursued.
14. In any case of incomplete graft incorporation and/or tendon exposure, further photo documentation will be obtained by the patient, family, or home health or wound team, or physician until epithelialization is complete and further wound care is no longer needed. Details of continued follow-up visits and methods of further documentation will be individualized so as to minimize excessive demands on patient resources.
15. Photos of donor sites at each time period will be submitted for evaluation by two independent surgeons who possess expertise in evaluation of free flap donor site wounds and skin grafts but who will not be involved in enrollment of patients in this trial or of management of their wounds. The percentage of graft incorporation and presence or absence of tendon exposure will be documented by each physician in a blinded fashion. The independent surgeons will also rate donor site graft aesthetic appearance on a 1-10 scale in a blinded fashion. Time to

complete epithelialization will be determined by the treating physician, and photo documentation will be submitted for blinded review by the independent surgeons. Any case of failed epithelialization that does not completely epithelialize within 90 days after surgery will be categorized as “greater than 90 days for analysis”, and all study-related patient contact will cease at that time.

16. Descriptive statistics will be reported. Univariate statistics will be used to compare primary and secondary outcomes between groups.

Premature Termination of Study:

This study may be prematurely terminated by the study team at any point if outcomes appear unequivocally worse than standard of care, if unusual types or rates of complications occur, or if any other safety concerns arise. An interim analysis will be performed in order to assess comparative outcomes following successful treatment of 20 subjects and determine whether to proceed with the remainder of the study.

Variables:

1. Surgical harvest technique will not be standardized between surgeons with the exception of requiring suprafascial harvest overlying the area to be grafted.
2. Donor site of split-thickness graft will be at surgeon discretion.
17. Utilization of purse string suture or other methods to narrow the flap donor site wound prior to grafting.
18. Decision to pursue secondary wound care strategy will be at surgeon discretion, including timing and type of treatment.

Funding Source and Funding Needs:

All Restrata products will be provided at no cost to patients by Acera Surgical Inc. No additional financial resources will be necessary to support this project.

Background Information:

Restrata (Acera Surgical, St. Louis, MO) is a synthetic hybrid-scale fiber matrix that possesses a fibrous structure of varying fiber diameters with high porosity [1]. The architecture of the material, which is similar to native extracellular matrix, allows for cell ingress and retention, as well as neovascularization of newly forming tissue, before completely degrading via hydrolysis [1]. The electrospun matrix is composed of two synthetic biocompatible polymers, polyglactin 910 (PLGA 10:90) and polydioxanone (PDO), both of which are used in other (FDA)-cleared devices, including dura substitutes, resorbable sutures, and orthopedic implants [1]. PLGA 10:90 and PDO were specifically selected in order to achieve a matrix with optimal handling properties and a rate of resorption ideally matched to the process of new tissue formation and wound healing. These polymers are co-electrospun into soft, white, compliant, non-woven sheets capable of supporting the natural wound healing process [1]. Once applied to a wound, the matrix supports cellular infiltration, new tissue formation, and wound healing while progressively resorbing into the tissue over the course of two weeks, on average.

Multiple clinical studies, including retrospective analyses, prospective analyses, and case reports have been conducted to evaluate the clinical efficacy of the synthetic hybrid-scale fiber matrix across multiple use cases in the wound care setting. A summary of the clinical studies and

outcomes can be found in the table below [2-17]. Assessment of over 150 treated wounds of varying etiologies demonstrated that significant wound healing was observed following treatment with the synthetic hybrid-scale fiber matrix across multiple wound types and clinical use settings. Results further demonstrate that the electrospun hybrid-scale fiber matrix also offered unique clinical versatility in facilitating both tissue granulation and a bridge to skin grafting as well as definitive wound closure and re-epithelialization, unlike alternative synthetic scaffolds and matrices.

Published rates of skin graft failure in forearm reconstruction range from 13-38% [18-20]. This occurrence prolongs healing, requires multiple additional health care encounters, and may result in worse aesthetic or event outcomes, sometimes requiring physical therapy. Patients have multiple complex medical needs following head and neck free flap reconstruction, and improving forearm reconstructive outcomes would undoubtedly be beneficial in this setting. Wound care matrices have been investigated in forearm flap reconstruction. Wester et al compared use of STSG alone to the combination of acellular dermal matrix AlloDerm (Allergan, Madison, NJ) in combination with STSG [21]. They noted improved cosmesis, similar rates of graft failure, and no cases of secondary graft requirement in the AlloDerm + STSG group. Other studies have investigated use of matrices alone or in a staged fashion with grafting [22-25]. Restrata has not previously been studied for this purpose, and in light of the positive outcomes in other similar wounds, investigation of its application to this purpose is relevant.

Clinical indication	# of wounds	Patient demographics	Treatment method	Outcomes	Adverse events	Reference
Chronic wounds (DFUs, VLUs, PUs, traumatic and postsurgical wounds, nonvenous vascular wounds, necrotic wounds)	82	48% male; average patient age 72 years; average wound age 36 weeks; average wound surface area 3.4 cm ²	Multiple applications of the synthetic hybrid-scale fiber matrix as needed for up to 12 weeks	85% complete wound closure at 12 weeks and significant reduction in local inflammation	None	[2]
Recalcitrant neuropathic foot ulcers	4	100% male; patient age range 67-73 years	Weekly, or as appropriate, treatment with synthetic hybrid-scale fiber matrix followed by adjunctive therapy	75% complete wound closure and successful limb preservation	None	[3]
DFUs	24	90% male; average patient age 55 years; average ulcer duration 16 weeks; average ulcer surface area 4.4 cm ²	Weekly, or as appropriate, treatment with synthetic hybrid-scale fiber matrix for up to 12 weeks	75% complete wound closure at 12 weeks	None due to synthetic matrix	[4]

Chronic wounds (DFU, VLU, PUs, Charcot foot deformity)	5	80% male; average patient age 66 years; average ulcer duration 51 months	Multiple applications of the synthetic hybrid-scale fiber matrix as needed in conjunction with NPWT	Formation of granulation tissue, coverage over exposed structures, and reduction in wound size	None	[5]
PUs	11	64% male; average patient age 55 years;	Single application of synthetic hybrid-scale fiber matrix as a foundation for rotational skin flap	Successful granulation tissue formation and preparation of wound site for flap reconstruction, with eventual wound closure rate of 90.9%	None	[6]
Chronic wounds (DFUs, VLUs)	23	60% male; average patient age 68 years; average ulcer duration 16 months	Weekly, or as appropriate, treatment with synthetic hybrid-scale fiber matrix	96% complete wound closure at 21 weeks	None due to synthetic matrix	[7]
TMA wounds	20	85% male; average patient age 62 years	10 wounds treated with synthetic hybrid-scale fiber matrix to augment closure of the suture line and 10 control nonaugmented wounds with standard primary closure	80% complete wound closure following treatment with synthetic matrix; reduced time to healing (18%), compared to control	Wound dehiscence (5), limb loss (2)	[8]
Post-Mohs wounds	10	Patient age range 63-90 years	Multiple applications of the synthetic hybrid-scale fiber matrix as needed	Effective re-epithelialization and wound closure with minimal scarring	Infection (1)	[9]
Post-Mohs wounds	4	75% male; average patient age 78 years; average ulcer surface area 11.5 cm ²	Multiple applications of the synthetic hybrid-scale fiber matrix as needed	100% complete wound closure in 8 weeks with no scars or skin deformities	None	[10]
Peroneal tendon healing	12	25% male; patient age range 18-75 years	Peroneal tendon repair augmented with synthetic hybrid-scale fiber matrix	Significant reduction in pain and rapid return to normal activity	None	[11]

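### A repeat graft placed before week four can be scored as take of the index graft, and an exposed tendon re-covered by then is scored as not exposed

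*Protocol*

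**What the plan says.** The treatment under test is the index operation. The Intervention section defines it as "Reconstruction of forearm harvest site using Restra with a split-thickness skin graft", and the control is the graft alone.

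Both primary outcomes are states at one time point: "Tendon exposure at four weeks post-operatively (Yes/No" and "Percentage of surface area of split-thickness skin graft incorporation at four weeks post-operatively". Under Protocol step 15, two independent surgeons who do not manage the wounds read exposure and incorporation from photographs, blinded.

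Surgery on the same wound is allowed before that reading. Step 13 begins "If at any point the treating physician feels that the primary treatment strategy is inadequate or inappropriate" and continues that "a secondary wound care strategy (alternative treatment, negative pressure therapy, surgical debridement, repeat grafting, etc) may be pursued". Variables item 18 adds: "Decision to pursue secondary wound care strategy will be at surgeon discretion, including timing and type of treatment". Blinding is stated for the photograph readers; none is stated for the treating surgeon.

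The wound is first seen early. Step 7 says "Bolsters are removed at five days, the wound is inspected, and high-definition digital photographs are obtained". For the next visit, step 9 says "Any visit between 12 and 16 days will be considered acceptable as two-week follow-up". Step 10 makes a dressing the first-line response to graft failure by two weeks, and step 12 does the same at four weeks.

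Two-week exposure, two-week incorporation, and re-operation or secondary wound care after tendon exposure are secondary outcomes 1, 2 and 5. Nothing in the protocol links them to the scoring of the primary outcomes.

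**The concern.** The primary outcomes are meant to show how the index reconstruction did. Once a wound has been re-grafted, the four-week photograph shows the index reconstruction plus a second operation whose use and timing were discretionary.

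Two consequences follow. First, primary outcome 2 does not say which graft is meant. A reader who sees well-taken graft at week four may score it as incorporated even where the index graft was lost and replaced. The protocol does not say that readers are told of re-interventions, or what to do if earlier photographs suggest one. Blinding does not help, because the reader can describe the photograph correctly and still credit the wrong graft. Second, primary outcome 1 taken literally scores a tendon that was exposed and surgically re-covered before week four as not exposed.

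What is at stake is the preliminary effect estimate. The Goal Enrollment section concedes that the trial cannot really test its hypothesis and justifies the small sample by the need for preliminary data, so that estimate is its main product.

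**Working it through.** **The plan's own figure.** Goal Enrollment gives 25% versus 10%, 80% power, alpha 0.05 and 100 per arm. With a two-sided test, pooled variance and no continuity correction:

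n = [1.96·√(2·0.175·0.825) + 0.8416·√(0.25·0.75 + 0.10·0.90)]² / 0.15² = (1.0532 + 0.4434)² / 0.0225 ≈ 99.5, so 100 per arm.

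The figure reproduces and is not in dispute.

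**Weight of one case, primary outcome 1.** Enrolment is 40 patients at 1:1, so 20 per arm. One patient is 1/20 = 5 points, and 5/15 is one third of the target difference. Expected exposures are 20 × 0.25 = 5 (control) and 20 × 0.10 = 2 (intervention).
- One control case re-covered: 4/20 versus 2/20, a difference of 10 points.
- One intervention case re-covered: 5/20 versus 1/20, a difference of 20 points.

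**Weight of one case, primary outcome 2.** If the repeat graft takes and is credited, the arm mean rises by up to (re-grafted % of the wound)/20. For 20%, 50% and 100% re-grafted this is 1, 2.5 and 5 points. If readers credit only the index graft, the shift is zero.

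**Time available.** Taking week four as day 28, 28 − 16 = 12 to 28 − 12 = 16 days remain after the two-week visit, and 28 − 5 = 23 days after the five-day inspection.

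**How many cases.** The protocol gives no rate. Assume a share s of exposed wounds is surgically re-covered before week four, equal in both arms, and that re-coverage always hides the tendon. The 25% and 10% can be read in two ways:
- (a) All exposures up to week four. Expected cases = 7s; P(at least one) = 1 − (1 − 0.25s)^20 · (1 − 0.10s)^20.
- (b) The week-four state after re-coverage. Replace s by s/(1 − s) in both formulas.

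| s (assumed) | Expected cases, (a) to (b) | P(at least one), (a) to (b) |
|---|---|---|
| 5% | 0.35 to 0.37 | 29.7% to 31.0% |
| 10% | 0.70 to 0.78 | 50.7% to 54.5% |
| 20% | 1.40 to 1.75 | 76.1% to 83.4% |

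These figures cover exposed wounds only. Repeat grafting for graft loss without exposure would add cases for primary outcome 2; the documents give no basis for a number.

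**The case against.** The strongest reply is that this is a gap in detail rather than an error. Handling of events between surgery and outcome is often left to an SAP, which is not at hand. The hypothesis itself names exposure at four weeks, so scoring that state whatever care came before is a legitimate treatment-policy comparison. For primary outcome 2, the graft named in both arms is the index graft and step 13 names repeat grafting separately, so the index graft is the natural reading. Secondary outcomes 1, 2 and 5 and the serial photographs would reveal most exposure cases, and with 40 patients each could be listed.

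Much of this stands. It is why primary outcome 1 should not be redefined. A reader might infer that any early re-coverage ought to count as exposure in the main score. The documents do not require that. It would put an unblinded surgeon's decision into a blinded outcome. It would also score two equal early exposures differently, according to whether the wound was re-grafted or closed on dressings.

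A reader might also infer a serious loss of power. If two of five control exposures and no intervention exposures were re-covered, the rates would be 15% versus 10%, and power at 20 per arm would fall from about 23% to 7%. That needs a 40% share in one arm only, for which the documents give no support, and power is not what this trial relies on.

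Two things survive the reply. The natural reading of outcome 2 is not written down, and blinded readers of a four-week photograph cannot apply it unaided. Secondary outcome 5 can be read as limited to treatment after tendon exposure, so a repeat graft for loss without exposure may not be captured. A later SAP cannot recover a re-grafted area or date that was never recorded.

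**Conclusion.** The point holds as a low-cost improvement. As written, the plan can credit a repeat graft's take as incorporation and can score a surgically re-covered tendon as not exposed. Each case is worth 5 points on the exposure difference and up to 5 points on an arm's mean incorporation.

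The number of cases is unknown and probably small. Under assumed shares of 5% to 20%, between about 0.4 and 1.8 exposed patients in the whole trial would be affected. Those shares are illustrations, and the probabilities attached to them should not be read as forecasts.

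A reader might infer a bias in favour of the device. The documents do not support a direction: re-coverage in the control arm shrinks the apparent benefit, and in the intervention arm it enlarges it. Nor do they show that the primary comparison is invalid. The harm is limited to the preliminary estimate.

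**What to change.** Change scoring and recording only; care stays as it is.

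1. State that primary outcome 2 refers to the index graft. Any area re-grafted before the four-week photograph counts as not incorporated, and the rest is read from that photograph. Debrided area is not automatically counted as failed.
2. Record the date, type, reason and area (square cm) of every secondary intervention before week four, with or without tendon exposure. List these cases by arm beside the primary results.
3. Keep primary outcome 1 as the blinded four-week photographic state. Add a prespecified supplementary analysis that also counts as exposed any patient in whom the blinded readers saw tendon on an earlier planned photograph and whose site was surgically re-covered before week four.

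The cost is a few sentences and one short form. Steps 7, 9, 11 and 14 already plan the photographs, step 15 already sends those from each time period to the readers, and wound surface area is already a recorded covariate. There are two downsides: the re-grafted area comes from an unblinded record, and the incorporation figure may be slightly lower. If no wound is re-grafted or surgically re-covered before week four, the results do not change.

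### Secondary outcome 4 compares healing time only among patients whose tendon became exposed, an event after randomisation that the matrix is expected to reduce; it should be reported descriptively, not compared between arms

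*Protocol*

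**What the plan says.** Under Secondary Outcomes, item 4 restricts healing time to a subset: "In patients with tendon exposure, time to complete wound epithelialization (measured as time from surgery to first documentation of complete epithelialization in days". It does not say at which visit exposure must be present. The event that defines the subset, assessed at four weeks, is primary outcome 1: "Tendon exposure at four weeks post-operatively (Yes/No". The Randomization section places allocation at the scheduling of surgery, so exposure can only come afterwards.

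Goal Enrollment gives the expected effect on that event: "25% baseline, 10% expected rate with intervention with power of 80% and alpha 0.05". It sets the sample at 40 patients, 1:1, and concedes that "this design is not truly hypothesis testing".

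In the Protocol section, step 16 states: "Univariate statistics will be used to compare primary and secondary outcomes between groups". Outcome 4 is not exempted. Step 11 sets the last photograph scheduled for everyone: "High-definition digital photographs are obtained at four-week follow-up". Step 14 goes further only for some: "In any case of incomplete graft incorporation and/or tendon exposure, further photo documentation will be obtained". Step 15 fixes the upper limit: "Any case of failed epithelialization that does not completely epithelialize within 90 days after surgery will be categorized as" exceeding 90 days. No healing-time outcome is listed for all randomised patients.

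**The concern.** If the hypothesis is right, the exposed controls include patients whom the matrix would have protected, while the exposed Restrata patients are those it did not protect. Randomisation balances the arms but not these two subsets. If the matrix mainly prevents exposures that would have healed quickly, the remaining Restrata cases look slow. If it mainly prevents slow ones, they look fast. Either pattern can appear when the matrix does nothing to healing once a tendon is exposed. A larger sample would not remove this.

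At stake is the reading of one secondary outcome. Followed literally, step 16 yields a between-arm difference that could be taken for a treatment effect when it reflects which patients became exposed. A later, larger trial that reused the outcome would inherit the problem.

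**Working it through.** **Inputs from the protocol.** 20 patients per arm (40 at 1:1); exposure 25% control and 10% Restrata; power 80%, alpha 0.05; follow-up limit 90 days.

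**The plan's own figure.** With pooled variance, two-sided, no continuity correction:
n = [1.960·√(2·0.175·0.825) + 0.842·√(0.25·0.75 + 0.10·0.90)]² / 0.15² = (1.053 + 0.443)² / 0.0225 ≈ 99.5, so 100 per arm. This matches the protocol, so the two rates are used below as intended.

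**Numbers compared, if exposure means exposure at four weeks.**
- Control: 20 × 0.25 = 5. Restrata: 20 × 0.10 = 2.
- Chance of no exposed Restrata patient: 0.90²⁰ = 0.122. At Restrata rates of 15% and 20% it is 0.039 and 0.012.
- Smallest two-sided exact rank p-value at 5 against 2: 2 / C(7,2) = 2/21 = 0.095.
- If exposure at any visit counts, the subset is the same size or larger. At 5 against 3 the minimum is already 2 / C(8,3) = 2/56 = 0.036, so this bound belongs to the expected counts only.

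**Possible bias (illustration; the protocol gives no healing times).** Assume the matrix causes no new exposures and does not change healing in those still exposed. Let f = Restrata rate / 0.25 be the share of exposures that remain, and r the correlation (Gaussian copula) between healing time and the tendency to stay exposed despite the matrix. The chance that a random exposed Restrata patient heals later than a random exposed control is
P = Pr(U > 0, Z > c) / f, with corr(U, Z) = r/√2 and c = Φ⁻¹(1 − f).
No difference is 0.50.

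| Restrata rate | f | r = 0 | r = 0.3 | r = 0.5 |
|---|---|---|---|---|
| 10% | 0.4 | 0.500 | 0.582 | 0.639 |
| 15% | 0.6 | 0.500 | 0.555 | 0.593 |
| 20% | 0.8 | 0.500 | 0.530 | 0.550 |

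Negative r gives one minus these values. Ties in the over-90-days category would pull P towards 0.50.

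In days at f = 0.4, if control healing times are uniform, the shift is (P − 0.5) × width:
- days 28–90 (width 62): 5.1 and 8.6 for r = 0.3 and 0.5
- days 28–60 (width 32): 2.6 and 4.4
- days 28–50 (width 22): 1.8 and 3.1

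**Bias against noise.** For width 62 the SD is 62/√12 = 17.9 days. With 5 against 2 the standard error is about 17.9·√(1/5 + 1/2) = 15.0 days. The shifts of 5.1 and 8.6 days are 0.34 and 0.57 of that. Shift and SD both scale with width, so the ratios hold for the narrower spreads.

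**A starker assumption.** Suppose exposures that the matrix cannot prevent (10% of patients) heal in 75 days, and preventable ones (15%) in 60, 50 or 45 days. The control mean is (10·75 + 15·b)/25 = 66, 60 or 57 days against 75 for Restrata: 9, 15 or 18 days slower with no true effect, and 0 if both types heal in 75 days. The size depends entirely on what is assumed.

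**The case against.** Four points can be made for leaving the plan alone.

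*The study is preliminary.* The objective and hypothesis speak of association, and the protocol disclaims hypothesis testing. This lowers the severity. It does not answer the point, because the disclaimer follows from the sample-size discussion and concerns power, not selection, and step 16 still plans the comparison.

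*Noise swamps the bias.* At 5 against 2, with a standard error near 15 days, the correlation illustration stays well below one standard error, and a rank test could not reach 0.05. This stands for the expected counts. It weakens if exposure at any visit counts, and a small sample does not make the comparison valid. It also means that little is lost by dropping the test.

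*Healing is compared elsewhere.* Primary outcome 2, graft incorporation at four weeks, is not restricted to exposed patients. This stands, and it limits what depends on outcome 4.

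*This belongs in the analysis plan.* The protocol itself fixes both the exposed-only population and the comparison, so an analysis plan that follows it inherits the problem.

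A reader might also infer that outcome 4 is biased against Restrata, or in its favour. The documents support neither: they give no healing times and do not say which exposures the matrix would prevent.

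**Conclusion.** The point holds and is minor. As written, the plan compares arms within a subset defined by an event after randomisation that the treatment is expected to change 2.5-fold (25% against 10%). Attributing a difference there to the matrix requires that prevention of exposure be unrelated to healing speed, which these data cannot test. If that assumption holds, the bias is zero.

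The expected counts rest on the protocol's own rates and on exposure at four weeks. Every figure for the bias rests on assumed healing times and is illustration only.

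Two stronger readings should be resisted. One is that a difference in outcome 4 could never reflect the matrix: it could, but the comparison cannot show it. The other is that the trial's main results are compromised: neither primary outcome is conditioned on exposure, and the protocol announces no treatment-effect claim for outcome 4.

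**What to change.** **Change to make.** Add one sentence to step 16: secondary outcome 4 is excluded from the between-group comparison and is summarised descriptively by arm, with the exposure time point named and no between-arm test or treatment-effect claim. The cost is the loss of a test that has almost no power at the expected counts.

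**Optional, if the sponsor wants a randomised comparison of healing.** Compare complete epithelialisation in all randomised patients using photographs already scheduled, for example the proportion completely epithelialised at the four-week visit. This needs a yes/no judgement for every patient at that visit and partly overlaps primary outcome 2. It also answers a different question from how long healing takes once a tendon is exposed.

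Use time to epithelialisation up to day 90 in all patients only if everyone not epithelialised at four weeks is followed until healed or day 90, with those unhealed at day 90 ranked last and a method that allows for ties. Step 14 does not cover a graft that is fully incorporated but not yet epithelialised, so such patients would need later photographs. About 40 − 7 = 33 patients are expected to have no exposure at four weeks; if 5% to 30% of them were in this position (assumption), that is about 2 to 10 patients.

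Do not censor these grafts at their four-week photograph. Follow-up would then end near day 28 for good takes and run to day 90 for failures, so censoring would depend on an outcome the matrix is expected to affect, which brings the same problem back.
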